8.7.7 Duration of Treatment and Number of Dressing Changes Analysis

Duration of Treatment: defined as the time in day(s) from the date of TKA revision to the end of treatment and is calculated as:

DOT= (Date of end of treatment – Date of the TKA revision)

Subjects who have their end of treatment on the same day of TKA revision after receiving initial dressing application will be considered to have a duration of treatment of 0.5 days. If subjects did not receive the initial dressing application, then the duration of treatment will be 0 days.

Treatment duration and number of dressing changes will be calculated and summarized by treatment arm, and then will be compared using a 2-sample t-test or Wilcoxon Rank-Sum test as appropriate.

8.7.8 Healthcare Utilization Analysis

The TKA revision related readmission (Yes/No) to hospital after discharge will be summarized by treatment arm and will be compared using a Fisher's exact test or Chi-Square test as appropriate.

All healthcare utilization parameters that related to the TKA revision including:

- number of home health visit(s)
- number of clinic visit(s)
- number of rehab or physical therapy visit(s)
- number of all healthcare visit(s) (number of home health visit(s) + number of clinic visit(s) + number of rehab or physical therapy visit(s))
- total length of hospital stay (days) after readmission
- number of day(s) spent in the ICU after readmission

Each healthcare utilization parameters will be accessed at visits of End of Treatment, Midterm Follow-up, and Long-Term Follow-up and unscheduled. These parameters will be summarized by treatment arm and compared using a 2-sample t-test.

8.7.9 ciNPT Device Replacement Analysis

The number of replacements of ciNPT therapy unit and Prevena dressing and reasons for replacements will be listed and summarized using frequencies and percentages.

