4.11.3. Healthcare Utilization Assessment

Information related to additional hospital procedures and/or follow-up care after the subject's TKA revision during the study period will be documented at all post-surgery visits, scheduled or unscheduled. Data to be collected will include:

- Relatedness to the TKA revision
- Duration of stay for TKA revision
- Length of hospital stay (days)
- Days in ICU
- Re-admission after TKA revision (yes/no)
- Length of hospital stay (days)
- Days in ICU
- Number of home health visits after hospital discharge
- Number of clinic visits after hospital discharge
- Number of rehab/physical therapy visits

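### SAP 8.7.8 compares readmission and ICU days by an unstratified t-test with no fallback, counts only revision-related use, and plans no comparison of the index hospital stay

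*SAP*

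**What the plan says.** SAP 8.7.8 has two parts. The first covers readmission as a binary outcome: "The TKA revision related readmission (Yes/No) to hospital after discharge will be summarized by treatment arm", and it "will be compared using a Fisher's exact test or Chi-Square test as appropriate". The second opens with "All healthcare utilization parameters that related to the TKA revision including" and lists six items: home health visits, clinic visits, rehabilitation or physical therapy visits, the sum of these three, "total length of hospital stay (days) after readmission", and ICU days after readmission. For all six, "These parameters will be summarized by treatment arm and compared using a 2-sample t-test". No alternative test and no stratification are given.

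The section just before it, SAP 8.7.7, handles treatment duration and dressing changes differently: these "will be compared using a 2-sample t-test or Wilcoxon Rank-Sum test as appropriate".

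Protocol 4.11.3 collects relatedness to the TKA revision and "Duration of stay for TKA revision", with hospital and ICU days, separately from the days of any readmission. Both inpatient items in SAP 8.7.8 are limited to readmission. No other SAP summary covers the index stay, and SAP section 10 does not mention it.

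SAP 8.7 makes ITT the default set for exploratory analyses and says that those involving revision type use the actual type. Protocol 8.3.6 makes no multiplicity adjustment for exploratory analyses.

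**The concern.** Readmission and ICU days combine a rare event with a skewed duration. A t-test on such totals is driven by a few long stays, and a real difference can be lost in their variance. SAP 8.7.7 shows that the authors had a rank test in mind for durations and counts, and nothing explains why it stops there.

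Four further gaps lie in the same section:

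- **Revision type is ignored.** Randomization is stratified by it, and the assumed SSC rates differ widely (33% septic, 6.9% aseptic).
- **Only revision-related use is counted.** The trial is open-label, the assessor of relatedness is not named, and no adjudication is described.
- **The index stay has no comparison.** Randomization takes place after incision closure (Protocol 4.9), so the postoperative stay follows randomization and is a valid comparison between arms.
- **Totals and follow-up are undefined.** The SAP does not say how subjects without a readmission enter the day counts, or what happens to subjects whose observation ends early.

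Protocol 1.2 cites prolonged hospital stays and burden on the healthcare system as part of the case for the trial. SAP 8.7.8 is where hospital and visit use is compared.

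**Working it through.** **Arm size.** The documents give no sample-size figure for utilization, so the primary-endpoint size sets the scale. With 20% v 10%, two-sided 0.05 and 80% power:

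n = [1.960·√(2·0.15·0.85) + 0.842·√(0.20·0.80 + 0.10·0.90)]² / 0.10² = 198.96, so 199 per arm.

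This reproduces SAP 2.1. Inflating 398 gives 398/0.95 = 419 and 398/0.90 = 443, which bracket the planned 440.

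**Assumptions.** Neither document gives a utilization rate. Assumed: readmission 10% v 5%, or 15% v 7.5%; the same stay distribution in both arms, with mean 6 days if readmitted (1 plus a negative binomial with mean 5 and shape 1); all subjects counted, with zero if not readmitted.

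**t-test on days, by hand.** For a stay Y, E[Y] = 6 and Var(Y) = 5 + 5²/1 = 30, so E[Y²] = 36 + 30 = 66. With readmission probability p, total days have mean 6p and variance 66p − (6p)².

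- 10% v 5%: variances 6.24 and 3.21; difference 0.30 days; SE = √(9.45/199) = 0.218; ratio 1.377; power Φ(1.377 − 1.960) = 28%.
- 15% v 7.5%: variances 9.09 and 4.75; difference 0.45 days; SE = √(13.84/199) = 0.264; ratio 1.707; power Φ(1.707 − 1.960) = 40%.

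**Test of any readmission, by hand.** Power = Φ{[d − 1.960·√(2p̄(1−p̄)/n)] / √([p₁(1−p₁) + p₂(1−p₂)]/n)}.

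- 10% v 5%: Φ[(0.05 − 1.960·0.02641)/0.02629] = Φ(−0.067) = 47%.
- 15% v 7.5%: Φ[(0.075 − 1.960·0.03168)/0.03145] = Φ(0.411) = 66%.

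**Simulation** (4,000 trials per scenario, 199 per arm):

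| Readmission | t-test on days | Wilcoxon on days | Chi-square, any readmission |
|---|---|---|---|
| 10% v 5% | 29% | 47% | 48% |
| 15% v 7.5% | 41% | 67% | 67% |
| 20% v 10% | 53% | 79% | 80% |

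A second simulation with log-normal stays (median 5 days, sigma 0.8) gave 31% v 46% and 44% v 65% for t-test v rank test in the first two rows. The gap does not hinge on one distribution.

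**Type I error of the t-test.** 3.0% to 4.3% for readmission days at 2% to 20% readmission; 0.1% to 3.4% for ICU days at 0.5% to 2% use. It is conservative, not inflated.

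**Visit counts that are seldom zero** (negative binomial, shape 2). Means 15 v 12.5: t-test 66%, Wilcoxon 59%. Means 5 v 4: 74% v 67%. Here the t-test is the better choice.

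**Follow-up.** Protocol 4.15 requires withdrawal after further surgery through the study incision within 90 days, and Protocol 4.4.2 ends data collection at withdrawal. SAP 7.3 imputes nothing for utilization, and SAP 8.7.8 has no exposure term. Totals for some of the heaviest users would therefore be cut short and compared as if complete.

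**The case against.** Most of the case against is sound, and it sets the limits of the point.

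- **A reader might infer that all the t-tested counts are mostly zero.** The documents do not say so. Four of the six items are outpatient visits or their sum; for clinic and rehabilitation visits and the sum nothing supports it, and for seldom-zero counts the t-test did better. The point is confined to inpatient days.
- **A reader might infer that fewer readmissions on ciNPT could not show.** They could. The Yes/No comparison has its own Fisher or chi-square test, with power within about one point of the rank test on days. What is lost is information on days.
- **A reader might infer that days are compared among readmitted subjects only**, a subset formed after randomization. The wording leaves the denominator open, but the ITT default in SAP 8.7 points the other way. It needs one clarifying sentence.
- **A reader might infer a demonstrated bias in the relatedness call.** Relatedness here is to the operation, which both arms had, not to the dressing, and no assessor is named. The open-label setting makes bias possible; nothing shows its direction or size.
- **A reader might call this the trial's only economic evidence, or the index stay a dropped analysis.** No document describes it as economic evidence, other resource measures are summarized (dressing changes, device replacements, SSCs needing intervention), and the protocol collects the index stay without promising an analysis.

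Stratification is not universal in the exploratory set: the log-rank test in SAP 8.7.6 and the tests in 8.7.7 also omit it. However, 30-day SSC, pain, KOOS and PROMIS all account for revision type. The analysis is exploratory and no trial conclusion depends on it.

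**Conclusion.** The point holds for readmission and ICU days, as a minor improvement to an exploratory analysis. At assumed readmission rates of 10% v 5% to 15% v 7.5% and about 199 per arm, the specified t-test has roughly 30-45% power on readmission days, against 47-66% for a rank test. False positives are not increased, and the planned Yes/No test already captures most of the incidence signal.

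These figures rest wholly on assumed rates and stay distributions. At the ITT size of about 220 per arm (440/2), the first scenario gives 30% for the t-test on days and 51% for any readmission by the same formulas, so the gap stays much the same.

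The other gaps need no assumed rates: revision type is ignored, only revision-related use is counted in an open-label trial, the collected index stay has no comparison, and neither the denominator nor truncated follow-up is defined.

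**What to change.** Amend SAP 8.7.8 as follows:

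1. State that readmission hospital days and ICU days are totalled per ITT subject across visits, with zero only for subjects observed without use.
2. Compare inpatient days by a van Elteren test stratified by revision type (actual type, as SAP 8.7 already sets), with the mean difference and a bootstrap interval. Keep the mean comparison for visit counts; do not apply the rank test to every item.
3. Compare readmission (Yes/No) by a CMH test stratified by revision type.
4. Report all-cause use beside revision-related use, using the relatedness item already collected.
5. Add index length of stay and index ICU days by arm.
6. Account for follow-up time, for example with an offset or a rate per day observed, so that totals cut short by withdrawal are not treated as complete. This assumes that use after withdrawal would have resembled use before it, so also report the number withdrawn for reoperation by arm.

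The cost is SAP text and a few more table rows. No new data are needed, provided unrelated use was recorded, as the relatedness item implies. The downside is that all-cause counts include some use unrelated to the knee.

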8.7.10 Laboratory Test Analysis

Pregnancy tests results will be presented in listings only.

9 STATISTICAL ANALYSES OF SAFETY MEASURES

In general, the summary results of safety parameters will be based on descriptive statistics. If desired, statistical tests of selected safety parameters may be performed for exploratory purposes, and descriptive p-values comparing the two treatment groups will be provided. All Safety analysis set subjects will be evaluated for safety and will be accounted for in the summation.

9.1 Adverse Events

All treatment-emergent adverse events (TEAEs), which are defined as adverse events with onset or worsening of pre-existing condition on or after the initial dressing application through the course of the study, will be summarized. Number and percentage of treated subjects who experienced at least one adverse event in each system organ class by preferred term will be summarized. In any given category (e.g., system organ class or preferred term) a subject will be counted only once. The denominator for the calculation of percentages will be the number of subjects in the Safety analysis set.

The following summary tables and listings will be presented by treatment arm:

- Overview of all treatment-emergent adverse events (TEAEs)
- Incidence of all treatment-emergent adverse events (TEAEs) by system organ class and preferred term
- Incidence of all treatment-emergent adverse events (TEAEs) by system organ class, preferred term, and maximum severity
- Incidence of all serious adverse events (SAEs) by system organ class and preferred term
- Incidence of treatment-related TEAEs by system organ class and preferred term
- Incidence of treatment-related TEAEs by system organ class, preferred term, and maximum severity
- Incidence of treatment-related serious adverse events (SAEs) by system organ class and preferred term
- Listing of all treatment-related adverse events
- Listing of all treatment-related serious adverse events (SAEs)
- Listing of discontinuations: Subjects who discontinued from the study due to any adverse event
- Listing of deaths: Subjects who died of any cause during the study

10 CHANGES FROM PLANNED ANALYSIS

All changes made from planned analyses in the study protocol are listed below.

- For the interim analysis, per Section 8.4.5 of the study protocol, it was stated the increase to the final sample size would only occur if the interim results had conditional power of success $\geq 50\%$, would be subject to the restrictions in Chen et al. [2004]², and would not be considered statistically binding. To further clarify, an increase to the final sample size can occur if the conditional power is below 50%. If the sample size is increased when conditional power is $\geq 50\%$, a type I error rate would not be inflated as mentioned in Chen et al. [2004]². If the sample size is increased when conditional power is $< 50\%$, an adjustment will be needed to control the Type I error. The adjustment is outlined in Section 7.3 of the interim SAP.
- Per Section 8.1.3.2 of the study protocol, it was stated: For the subscale scores, four possible outcomes will be summarized and listed: i) Normalized numeric subscale score; ii) Assessment done but incomplete; iii) Discontinued study prior to assessment; iv) Assessment not done. Section 8.7.2 of this final SAP only have two possible outcomes: i) Normalized numeric subscale score calculated based on KOOS Scoring 2012; ii) Missing assessment score for any reason.
- Per Section 8.1.3.3 of the study protocol, it was stated: For each subscale, there are four possible outcomes: i) Raw numeric subscale score and converted t-score; ii) Assessment done but

incomplete; iii) Discontinued study prior to assessment; iv) Assessment not done. Section 8.7.3 of this final SAP will have two possible outcomes: i) Raw numeric subscale score and converted t-score; ii) Missing assessment score by any reason.

- Per Section 8.3.4 of the study protocol, it was stated: The difference between the proportions (ciNPT – SOC) and their corresponding asymptotic 95% confidence intervals will be computed. Section 8.5 of this final SAP made a clarification as: For the combined population, a Cochran-Mantel-Haenszel (CMH) test stratified by type of revision (Septic, Aseptic) will be used to compare the SSC incidence rates between two treatment arms based on the mITT analysis set. The odds ratio and its asymptotic 95% confidence interval will be computed. This test is equivalent to the test of difference for the proportions. ii) For the septic and aseptic subpopulations, a Chi-square or Fisher's test, as appropriate will be performed within each revision type for SSC incidence rates between treatment groups based on the corresponding mITT analysis set.

All changes made in the SAP version 2.0 comparing with planned analyses in the SAP version 1.0 are listed below.

- Section 8.5 and 8.6 were updated to specify whether actual or randomized revision type will be utilized. Additional analyses to include actual revision stratification for primary and secondary endpoint were added.
- Section 8.7.6 of the SAP version 2.0, it is updated to: Censoring will occur for the following: 1) Subjects who experience their first SSC on the day of TKA revision after initial dressing application will be considered to have a time to SSC of 1 day. 2) Subjects, who do not have any SSC assessment after initial dressing application and they withdraw before the first scheduled SSC assessment at the end of treatment, will be censored at the date of TKA revision. 3) Subjects who do not have any SSC assessment at Day 90 will be censored at Day 90 or end of study date, whichever comes first.
- MedDRA coding dictionary version was updated to be version 20.1 or higher.

12 APPENDIX: TABLES, FIGURES, AND LISTINGS

The tables, listings and figures will be provided in a separate appendix document.
